When inflated, the cuff constricts the urethra and blocks the passage of any urine. When deflated, the cuff reduces pressure on the urethra and allows for the free passage of urine.

[figure not shown]

Figure 5 AUS with Foley catheter

A foley catheter is also inserted during surgery, which is removed prior to discharge from the hospital. The artificial sphincter cuff is not inflated immediately after surgery, in order to allow the tissues to heal.

Significance:

Post-prostatectomy urinary incontinence is a troubling complication following treatment (radical prostatectomy, radiation therapy, or brachytherapy) for prostate cancer, or in rare instances the treatment of benign prostatic hypertrophy, and significantly decreases quality of life in affected patients. An artificial urinary sphincter has been found to significantly improve quality of life in these patients. Providing data which demonstrates the safety and feasibility to activate an artificial urinary sphincter 3 weeks after surgery as opposed to 4-6 weeks will allow men to regain their continence earlier, therefore improve their quality of life.

Methods

Study Design:

The design will be a single institute prospective study with patients undergoing artificial urinary sphincter placement by the operating surgeon, [name] at Charleston Area Medical Center in Charleston, WV. All patients following informed consent that meet the inclusion criteria are eligible to participate in the study.

Sample:

All male patients with moderate to severe urinary incontinence who have been treated for prostate cancer (radical prostatectomy, External Beam Radiation therapy or brachytherapy, or Incontinence related to trans urethral resection of the prostate (TURP) or simple prostatectomy undergoing artificial urinary sphincter placement at Charleston Area Medical Center by [name], D.O. will be offered the chance to participate in this study. This is a pilot study and thus no power analysis to calculate necessary sample size is conducted to determine a number that would yield sufficient power. We will aim to enroll 25 patients, which we anticipate to be accrued within 3 years from the start of the study. We will have 1 study group: those who are activated at 3 weeks post implantation.

Inclusion Criteria:

All patients undergoing artificial urinary sphincter (AUS) placement by a single surgeon, [name].

Exclusion Criteria:

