Any patient who has previously undergone artificial urinary sphincter placement and presents for revision or additional cuff placement.

Any patient who is undergoing combined artificial urinary sphincter and inflatable penile prosthesis placement.

Any patient who is a poor candidate for early activation due to poor condition at presentation or signs of infection.

Procedures and Protocol:

There isn't a comparison group for this study; therefore all patients agreeing to participate will have the urinary sphincter activated 3 weeks after surgery. If there are patients that later choose not to have early activation or are found to be poor candidates for three week activation based upon their post op

exam, we will proceed with activation at a 4-6 week time period. While there is no comparison group in the study, patient satisfaction and adverse events for study patients will be compared to historical literature.

Currently patients are not routinely seen for a 3 week follow up appointment, so approximately \$3000 will be requested from Research appropriations to cover the costs of this study. All other costs are standard of care, so patient will be responsible for those costs whether they agree to enroll in the study or not. The money from the CAMC Research Appropriations will be used to cover all the clinical fees for the 3 week visit to activate the AUS.

Pre-procedure:

- 1. All eligible patients will be informed about the study at their regularly scheduled pre-operative office visit. If the patient agrees to participate, they will be consented with the consent form as written. A note is made in the progress note of the patient's chart detailing the consent.
- Original signed consent will be kept and stored in the consent binder at [name] office and one copy of the consent will be placed in the medical record and another will be given to the participant.
- 3. Patient will complete an SF-8 quality of life survey and Incontinence Impact Questionnaire (Appendix A).

Intraoperative procedures:

1. Once consented, the patient will undergo the procedure without any changes to our normal routine. The patient's device will be deactivated at the conclusion of the procedure.

Post-procedure:

- 1. The patient will be discharged post-operatively (same day) and follow-up will be arranged in 3 weeks to activate the device.

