- 2. Study patients have a follow up office visit at 3 weeks (up to 3 weeks and 3 days after the procedure) which includes a post-operative evaluation of their incisions, degree of bruising, tissue induration, tenderness and accessibility of the pump. If these factors are acceptable and pump mechanics are normal, the artificial sphincter will be activated and the patient will be educated on its proper use.
- 3. Additional follow up will include the regular 6 week visit, a visit at 3 months, and then every 6 months for a total of 1 year unless issues arise that necessitates deviation. At each visit, patients will complete the Incontinence Impact Questionnaire and the SF-8 quality of life survey.

Study Chart:

INFORMATION	PRE-	Intra-	POST-Treatment	POST-	POST-	POST-	POST-Operative
	Treat	operative	3 weeks	OperativeTrea	Operative	Operative	Treatment 1 year
	ment	Treatment	(up to 3 weeks and	tment	Treatment 3	Treatment	(+ 1 month)
			3 days after	6 weeks	months	Six months	
			procedure)	(+ 1 week)	(+ 2 weeks)	(+ 3 weeks)	
Inform Subject	Х						
Consent Subject	Х						
Note in Record	Х						
Office visit	Х		Х	X	Х	Х	Х
SF-8 survey administered	Х			Х	Х	Х	Х
Incontinence Impact Questionnaire	Х		Х	Х	х	Х	Х
Procedure conducted		Х					
Data Collection	Х	X	Х	Х	Х	Х	Х

Data Collection and Management:

The SF-8 is a quality of life instrument related to health functioning that provides an eight question brief assessment of physical and mental health⁶. It has been found to have adequate reliability and validity in prior studies for quality of patient life and it incorporates a manual for easy interpretation.⁷. The Incontinence Impact Questionnaire short form was adapted from a survey that was developed for women with stress incontinence. This questionnaire has been validated for use in men after radical prostatectomies and consists of 7 items in which measures the effect of Urinary Incontinence on quality of life⁸.

Following surgery, patient characteristics and operative details will be recorded. These will include:

- Medical Record Number
- Patient name
- Age
- BMI
- Operative time
- Artificial sphincter cuff size
- Pressure-regulating balloon size
- Intra-operative complications (urethral injury, bleeding)
- Reason for AUS placement (Post-prostatectomy, Radiation therapy for prostate cancer, or Incontinence related to TURP)
- Finish date of prostate cancer treatment or TURP
- Preoperative daily pad usage
- Pre-surgery SF-8 survey

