- History of medication
- Date device is activated
- Comorbidities
- ECOG Score

- ASA Score
- Tobacco Use
- Diabetes

When the study patient follows up at 3 weeks postoperatively, we will assess for immediate postoperative complications:

- Post-operative urinary retention Y/N
- Bleeding Y/N
- Presence/concern for infection Y/N
- Presence/concern for urethral erosion Y/N

When any patient follows up at 6 weeks, 6 months, and 12 months postoperatively, we will assess:

- Postoperative daily pad usage
- Perceived improvement in incontinence (scale 1 (none) 10 (very satisfied))
- Presence/concern for infection Y/N
- Presence/concern for urethral erosion Y/N
- Post-surgery SF-8 surveys (6 weeks, 3 months, 6 months)

Statistical Analysis:

The Center of Health Service and Outcomes Research will conduct the data analysis. For this exploratory study, selection of appropriate statistical measure will be determined by CAMC Center for Health Education and Research Institute. Specific tests will be determined by whether the data is continuous or categorical. Descriptive statistics will be used as appropriate and comparisons will be done using student's T-test and chi-square test. In addition univariate and multivariate multiple logistic regressions will be used to determine which variables predict patient's outcomes. All comparisons will be done at 95% of level of significance.

I. Human Subjects

Study population: All patients undergoing artificial urinary sphincter (AUS) placement by a single surgeon, [name] at Charleston Area Medical Center.

Recruitment methods: All patients, following informed consent, that meet the inclusion criteria are eligible to participate in the study. Patients will be consented by the principal investigator only at time of usual surgical informed consent using the attached consent form. Consent will be obtained prior to the surgical procedure.

Benefits: Early activation of the artificial urinary sphincter will allow the patient to regain continence earlier.

Risks and discomforts: The principle risks of participation in this study will be the standard risks of the operation.

Less often, there are risks of bleeding, infection, urinary tract injury, device erosion, wasting away of muscle mass in the urinary tract, or loss of bladder control.

Occasionally, there are risks of persistent loss of bladder control or mechanical failure of device.

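### The analysis section names only Student's t-test and chi-square for comparisons, and no paired or repeated-measures method, although the outcomes with a baseline are measured before and after surgery in the same men

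*Combined protocol and SAP*

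**What the plan says.** **Design.** Methods, Sample: "We will have 1 study group: those who are activated at 3 weeks post implantation". Procedures and Protocol: "There isn't a comparison group for this study". On size, Sample states "We will aim to enroll 25 patients" and that "no power analysis to calculate necessary sample size is conducted".

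**Repeated measurement.** IIQ-7 and SF-8 are completed before surgery (Pre-procedure, item 3). For follow-up, Post-procedure item 3 says "At each visit, patients will complete the Incontinence Impact Questionnaire and the SF-8 quality of life survey". The Study Chart shows IIQ-7 at five post-operative visits (3 weeks, 6 weeks, 3 months, 6 months, 1 year) and SF-8 at four (not at 3 weeks). The data list includes "Preoperative daily pad usage", and pad use again at three post-operative visits (6 weeks, 6 and 12 months). Other places list fewer questionnaire visits; the counts here follow the chart.

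**Analysis.** Statistical Analysis plans descriptive statistics, says "comparisons will be done using student's T-test and chi-square test", and adds logistic regressions for predictors of outcome. Data type is the only stated basis for choosing a test, and the choice of suitable measure is left to the analysis centre. The section does not say which comparisons the two tests serve, or whether the t-test is one-sample, paired or two-sample.

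**The one comparison that is spelled out.** Procedures and Protocol: "patient satisfaction and adverse events for study patients will be compared to historical literature".

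**The concern.** With one group and a baseline value for IIQ-7, SF-8 and pad use, any estimate of change over time compares a man with himself. Two measurements on one man are usually correlated, and a test for change has to use that. A selection rule that looks only at data type gives no route to a paired t-test, a signed-rank test, McNemar's test or a repeated-measures model, and none of these appears in the document.

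For categorical outcomes the rule leads to chi-square. The ordinary chi-square test of independence would treat 25 before values and 25 after values as 50 separate men. For continuous outcomes the result depends on which form of t-test the analyst picks. If it is the two-sample form, the standard error ignores the correlation, so with positive correlation intervals are too wide and moderate changes can be missed. In a study of 25 men that is precision given away for nothing.

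**Working it through.** **1. Is there a planned figure to reproduce?** No. The target of 25 comes with no effect size, SD, correlation or power. The size of the problem can therefore only be shown over a range of assumptions.

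**2. Inputs.** From the document: n = 25, one group, and the section's 95% level, read here as two-sided alpha 0.05. Assumed: equal SDs before and after, normal data, a true change d in SD units, and within-man correlation rho.

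**3. Interval width.** In SD units:
- two-sample standard error = sqrt(2/25) = 0.283
- paired standard error = sqrt(2(1 − rho)/25) = 0.237 at rho 0.3, 0.200 at 0.5, 0.155 at 0.7

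The ratio of standard errors is 1/sqrt(1 − rho) = 1.20, 1.41, 1.83. The two-sample interval uses 48 degrees of freedom and the paired one 24, and the ratio of their t quantiles is 0.974. The width ratio is therefore 0.974/sqrt(1 − rho): 0.97 at rho 0, 1.16 at 0.3, 1.38 at 0.5 and 1.78 at 0.7.

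**4. Power and type I error of the t-test** (100,000 simulated trials per setting, both tests run on the same data):

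| rho | Two-sample type I error | Power at d = 0.5: two-sample vs paired | Difference | Power at d = 1.0: two-sample vs paired |
|---|---|---|---|---|
| 0 | 4.9% | 41% vs 40% | about −1 point | 93% vs 92% |
| 0.3 | 2.1% | 40% vs 53% | 13 points | 96% vs 98% |
| 0.5 | 0.7% | 38% vs 67% | 29 points | 98% vs 99.8% |
| 0.7 | 0.1% | 36% vs 87% | 52 points | 99% vs 100% |

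At d = 1.5 both tests have at least 99.9% power at every correlation tried. With positive correlation the two-sample test rejects too rarely, not too often.

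**5. Paired binary outcomes** (20,000 simulated trials per setting, n = 25, phi = correlation between the two binary values; rates assumed):

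| Before, after | phi | Chi-square | Exact McNemar | Asymptotic McNemar |
|---|---|---|---|---|
| 50%, 50% (type I error) | 0 | 6.4% | 2.4% | 4.2% |
| 50%, 50% (type I error) | 0.5 | 1.0% | 1.4% | 4.4% |
| 50%, 25% (power) | 0 | 48% | 33% | 42% |
| 50%, 25% (power) | 0.3 | 47% | 43% | 54% |
| 50%, 25% (power) | 0.5 | 46% | 56% | 76% |

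The type I error of chi-square moves with a correlation it ignores. Exact McNemar keeps its error below 5% in these settings but does not always have more power, so the reason to use it is validity.

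**6. The historical comparison.** This is 25 men against a published rate, which is a one-sample problem. Background gives 79% for men who were satisfied and used at most one pad a day. Under a true rate of 79%, the exact probability of 23 or more of 25 is 0.080, and of 24 or more 0.021. An observed 20 of 25 (80%) has an exact 95% interval of 59% to 93%. For an adverse event seen in 0 of 25, the interval runs from 0 to 13.7%.

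**The case against.** A reader might infer that the plan has chosen independent-groups tests for before-and-after data, so that its p-values and intervals are wrong and much of the power is lost. The documents do not support that.

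- Student's t-test includes the paired and one-sample forms. The section neither says two-sample nor ties the tests to before-and-after data, and it leaves the final choice to the analysis centre. If the paired form is used, the t-test figures above fall away.
- Not every comparison is within a man. Reason for implantation, diabetes, tobacco use and similar factors are recorded, and some men may be activated at 4-6 weeks. Contrasts between such subgroups are between different men, and t-test and chi-square are ordinary choices there, small cells aside.
- The only comparison spelled out is with published results. Post-operative complications and the 1-10 improvement scale have no pre-operative value, so pairing does not arise for them.
- Effects on continence may be large. Background cites 60% to 90% of men reaching at most one pad a day. Suppose none of 25 does so before surgery and 15 (60%) do afterwards. Chi-square gives p of about 0.000004, and exact McNemar gives 2 × 0.5^15 = 0.00006. The conclusion is the same.

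All of this stands, and it limits the point. What it does not answer is that the text names no method for change in IIQ-7, SF-8 or pad use, that its selection rule ignores dependence, and that ordinary chi-square does not suit paired categories on any reading. Leaving the form of the test to the analysis centre does not close that gap.

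**Conclusion.** The point holds in a limited form: outcomes are collected repeatedly on the same men, and the analysis section gives no method that handles this. Followed as written, it leads to an invalid test for paired categories and leaves the t-test's form open.

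The cost for continuous outcomes is conditional on the two-sample form being used. At an assumed change of 0.5 SD it runs from none (correlation 0) to about 52 power points (correlation 0.7). At 1 SD it is 2 points or less. Both the correlation and the effect size are assumptions. With positive correlation the error is conservative, so it would not produce false claims of improvement; the outcomes at risk are those with moderate changes.

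Because this is an exploratory pilot on safety and feasibility with no power claim, the point is a correction to make before analysis and not a critical defect.

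**What to change.** Revise the Statistical Analysis section to say:

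- Descriptive statistics are kept for all outcomes.
- Student's t-test and chi-square are used only for comparisons between different men.
- Change from baseline in IIQ-7, SF-8 and daily pad use is analysed within man, reporting the mean change and 95% CI at each visit. A linear mixed model (visit as a factor, random effect for man) uses all available visits. Paired t-tests are an acceptable simpler choice, but each drops men who missed that visit. Wilcoxon signed-rank is the sensitivity analysis.
- Paired binary outcomes, for example at most one pad a day before and after, use the exact McNemar test.
- For the comparison with historical literature, each proportion is reported with a one-sample exact binomial 95% CI beside a published rate that is named, with its source, before the data are examined.

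The cost is a paragraph of text and slightly more analysis work. It needs no new data, visits or patients.

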Early Activation of Artificial Urinary Sphincter: A Pilot study

Abstract:

Urinary incontinence or loss of bladder control is a troublesome issue for all affected patients. The causes of urinary incontinence and its treatment options vary widely. A commonly encountered reason for urinary incontinence in men is related to treatment for prostate cancer. These treatment options can range from surgical removal of the prostate, external beam radiation therapy, and/or brachytherapy, the insertion of radioactive implants directly into the tissue. Mild cases of incontinence are responsive to more conservative measures, but moderate to severe cases often require placement of an artificial urinary sphincter. Typically, these devices are left deactivated for a period of 4- 6 weeks following implantation to allow swelling to subside before use. We hypothesize that the device could be activated within an earlier timeframe without increasing the risk of complications. No studies to date have evaluated this; therefore we plan to conduct a prospective study in which we will activate the device 3 weeks after placement and monitor for complications.

Aim of the study:

To assess the safety and feasibility of early activation of an artificial urinary sphincter and assess whether or not this increases the risk of postoperative complications. We hypothesize that a period of 3 weeks should allow adequate time for the resolution of urethral and scrotal swelling following artificial urinary sphincter placement, and that activation of the device at that time, as opposed to traditional 4-6 weeks post-operatively, will lead to improved patient satisfaction with no increase in postoperative complications.

Background:

Urinary incontinence is one of the most common complications following surgical treatment of prostate cancer via radical prostatectomy. All patients will have this to some degree in the initial post-operative period, but it typically resolves over time as the newly created urethrovesical anastomosis heals. Wolin et. al reported a 59% rate of urinary incontinence at 6 weeks post-prostatectomy among studied patients¹. For the unfortunate patients who have persistent incontinence requiring the use of multiple pads per day in the absence of a bladder neck contracture or stricture, an artificial urinary sphincter (AUS) may be the best option to regain continence.

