The AUS was first introduced into practice in 1972 at the Baylor College of Medicine. Since that time, it has been found to effectively improve the quality of life of patients with post-prostatectomy urinary incontinence. In a recent analysis, 79% of patients report being satisfied and using no more than one pad per day². The device has undergone numerous revisions since its introduction and the current model, the American Medical Systems (AMS) 800, is widely implanted throughout the U.S. and worldwide. Several studies have been performed validating the AUS as a surgical treatment of post prostatectomy incontinence. There have been varying degrees of success documented in the literature secondary to the different definitions of success used, however, using the definition of zero to 1 pad per day, success rates have varied between 60% and 90% in modern series(3). The most common

complication is urinary retention, which can be managed with a urethral catheter. Less common complications include infection, device malfunction, and urethral erosion³.

The device (see figure 1) is placed in the operating room under general anesthesia. The device consists of a urethral cuff, pressure regulating balloon, and an activation pump and once activated, the urethral cuff will be closed at rest. The patient will squeeze the scrotal pump to open the cuff in order to void once the need arises. Patients are typically discharged the same day without a Foley catheter, unless unable to void in the recovery room. The device is typically left in the de-activated position to allow reductions in urethral edema and scrotal edema before the patient is allowed to manipulate the device. The device is routinely activated at 4-6 weeks post-operatively⁴. A literature review did not reveal any papers or guidelines that show that this period of de-activation of 4-6 weeks is actually required, though Baylor College of Medicine reports current practice of only waiting 4 weeks until activation⁵. There have not been any studies conducted indicating any negative consequences of activating the device early and there have been two or three patients at CAMC who have activated their device a few days post discharge from the hospital, against our advice.. These patients did not report any adverse events with early activation.

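### The planned multivariable logistic model and open-ended predictor screen, with no named outcome, visit or cap on terms, ask more than 25 men can support

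*Combined protocol and SAP*

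**What the plan says.** The Sample section describes a single-group pilot without a power calculation: "We will aim to enroll 25 patients". After descriptive statistics, t-tests and chi-square tests, the Statistical Analysis section adds: "In addition univariate and multivariate multiple logistic regressions will be used to determine which variables predict patient's outcomes". It calls the study exploratory, leaves the choice of methods to the analysis centre, and sets a level that I read as two-sided 5%.

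For the regression, the plan does not state:
- the outcome, or how pad counts and questionnaire scores would be made binary;
- the visit;
- the predictors, a maximum number of terms, or a selection rule.

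The Data Collection and Management section lists the candidate predictors, one of which has three categories: "Reason for AUS placement (Post-prostatectomy, Radiation therapy for prostate cancer, or Incontinence related to TURP").

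Two places bear on how many events to expect. The Background says that "using the definition of zero to 1 pad per day, success rates have varied between 60% and 90% in modern series"; this is context and the study does not adopt it as an endpoint. The Aim of the study is to "assess whether or not this increases the risk of postoperative complications". On complications the Background gives no rates. It names urinary retention as the most common, then adds: "Less common complications include infection, device malfunction, and urethral erosion".

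**The concern.** A logistic model is limited by the size of the smaller outcome group, not by the number of men. With few events and many terms, some combination of predictors splits events from non-events perfectly (separation). Maximum likelihood then has no finite estimate, and software may print enormous odds ratios or a convergence warning. With fewer terms the model may fit, but its coefficients are driven by a handful of men. A one-at-a-time screen with no cap has a different weakness: run over enough variables, it is likely to turn something up by chance.

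At stake is whether the pilot reports false or uninterpretable risk factors for incontinence or complications after early activation.

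**Working it through.** The plan gives no figure for this analysis, so there is none to reproduce. The check asks what 25 men can support.

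**1. Candidate terms** (Data Collection and Management). Leaving out name, record number and activation date, the list is: age, BMI, operative time, cuff size, balloon size, intra-operative complications, reason for placement, treatment finish date, pre-operative pads, pre-operative SF-8, medication history, comorbidities, ECOG, ASA, tobacco, diabetes. That is 16 items. Reason for placement has three levels and needs two terms, so entering everything takes at least 15 + 2 = 17 terms.

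**2. Events if the outcome is failure to reach 0–1 pad per day** (Background range, all outcomes observed).
- 90% success: 25 × 0.10 = 2.5 failures
- 80% success: 25 × 0.20 = 5 failures
- 60% success: 25 × 0.40 = 10 failures

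Events per term at 10 failures: 10/17 = 0.59, 10/12 = 0.83, 10/5 = 2.0, 10/3 = 3.3. At 2.5 failures and 17 terms: 2.5/17 = 0.15.

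**3. Separation.** Datasets of 25 men were simulated with pure-noise predictors (normal, or binary with 30% prevalence). Each was tested by linear programming for a finite estimate, with 400–1,000 datasets per cell; ranges span repeat runs. Percentage with no finite estimate:

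| Terms | 3 failures | 5 failures | 10 failures |
|---|---|---|---|
| 3, one binary | 35–39 | 15–20 | 2–3 |
| 3, all continuous | 3 | 0.3 | 0 |
| 5, two binary | 67–70 | 33–35 | 6–8 |
| 5, all continuous | 23 | 5 | 1 |
| 12, half binary | 99–100 | 96–97 | 63–65 |
| 16, half binary | 100 | 100 | 97–98 |
| 17, about half binary | 100 | 100 | 99 |

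For small models the predictor type matters a great deal. At 12 terms it matters little: all-continuous predictors lower the figures by only a few points, to about 57% at 10 failures.

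**4. Events if the outcome is a complication.** The documents give no rate, so I assume 2–20%, with the chance of at most one event from the binomial with n = 25.

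| Assumed rate | Expected events | P(0 or 1 event) |
|---|---|---|
| 2% | 0.5 | 91% |
| 5% | 1.25 | 64% |
| 10% | 2.5 | 27% |
| 20% | 5 | 3% |

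A composite that includes retention could exceed 5 events. With one event, any model containing a binary term separates, because the single event falls in one category. Three continuous terms separate in about 51–56%.

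**5. Chance findings from the screen.** P(at least one p < 0.05) = 1 − 0.95^k for k independent noise variables: 1 − 0.95^12 = 46.0%; 1 − 0.95^16 = 56.0%. In simulation with 12–16 variables the rate depends on the test. Likelihood-ratio tests gave 47–69% at 3–10 failures. Wald tests gave 22–37% at 5–10 failures and only 5–6% at 3, where that test is very conservative. The plan names neither.

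**6. One pre-named predictor, most favourable case (10 failures).** These are approximate standard errors of the log odds ratio.
- Continuous, per SD: 1/√(25 × 0.6 × 0.4) = 0.408. The 95% limits are the estimate multiplied or divided by exp(1.96 × 0.408) ≈ 2.2.
- Binary, evenly split: √[(1/12.5 + 1/12.5)/(0.6 × 0.4)] = 0.816. The factor is exp(1.96 × 0.816) ≈ 4.9.

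Such a model can be estimated, though imprecisely.

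**The case against.** The best defence is that this is an exploratory pilot, that methods are left to the analysis centre, and that a competent analyst would not enter every variable. Much of that stands. Nothing says that all 17 terms go in, and at 10 failures a three-term model separates in only 0–3% of datasets. But the exploratory label does not supply an outcome or a cap, and the section still commits to running these regressions to determine predictors. Leaving the choices open means that they may be made after the data are seen.

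A reader might infer four stronger things, which the documents do not support:
- *That the regression cannot yield anything usable.* Small models often fit, and one pre-named predictor is estimable.
- *That small models fail at one fixed rate.* At 3 failures, 3–5 terms separate in anything from 3% to 70%, depending largely on how many predictors are binary. Several recorded items, such as age, BMI and operative time, can enter as continuous.
- *That complications will number only one to three.* No rate is given, and retention, named as the most common complication, is recorded at 3 weeks.
- *That about half of all such screens will produce a false predictor.* That is the nominal figure; with very few events, Wald tests give far less.

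**Conclusion.** The concern holds for the multivariable model and the uncapped screen. It does not hold for a single pre-named predictor. At 12–17 terms the model has no finite estimate in about 95–100% of noise datasets at 3–5 failures and about 57–99% at 10. At 3–5 terms the ranges are about 3–70%, 0–35% and 0–8% at 3, 5 and 10 failures; models that do fit have at most about 3 events per term. The nominal chance of at least one false predictor is 46–56%.

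These figures assume independent noise predictors, complete follow-up of 25 men, and a pad-based outcome that the study has not adopted. Any loss to follow-up would tend to lower the event counts. For complications, about 0.5–5 events or more is my assumption.

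This is worth changing before analysis, but the damage is confined to a secondary exploratory output. A reader should not infer that the descriptive safety result is compromised.

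**What to change.** In the Statistical Analysis section, delete the multivariable logistic regression and the uncapped univariate screen. Replace them with one of the following:

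1. Outcomes reported descriptively by key characteristics, with exact 95% confidence intervals for proportions. For example, 0/25 gives an upper limit of 1 − 0.025^(1/25) = 13.7%, so 0–13.7%.
2. At most one pre-named predictor of one named binary outcome at one named visit, fitted by a Firth or exact method, reported with its confidence interval and labelled hypothesis-generating.

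The cost is a few sentences, with no new data or visits. What is lost is an exploratory predictor analysis.
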